2.8 Safety analyses

All safety analyses will be based on the safety set. All listings and tables will be presented separately for the well-differentiated NET and the poorly-differentiated GEP-NEC groups. In addition, pooled safety analyses based on all patients will be produced.

2.8.1 Adverse events (AEs)

AE summaries will include all AEs occurring during on treatment period. Additional summaries will be displayed to report all AEs, AEs related to study treatment, all SAEs and SAEs related to study treatment collected up to 150 days after last administration of PDR001. All AEs collected in the AE (e)CRF page will be listed along with the information collected on those AEs e.g. AE relationship to study drug, AE outcome etc. AEs with start date outside of on-treatment period will be flagged in the listings.

AEs will be summarized by number and percentage of subjects having at least one AE, having at least one AE in each primary system organ class (SOC) and for each preferred term (PT) using MedDRA coding. A subject with multiple occurrences of an AE will be counted only once in the respective AE category. A subject with multiple CTCAE grades for the same preferred term will be summarized under the maximum CTCAE grade recorded for the event. AE with missing CTCAE grade will be included in the 'All grades' column of the summary tables.

In AE summaries, the primary system organ class will be presented alphabetically and the preferred terms will be sorted within primary SOC in descending frequency. The sort order for the preferred term will be based on their frequency in the investigational arm.

The following adverse event summaries will be produced using the safety set; overview of adverse events and deaths, AEs by SOC and PT, summarized by relationship, seriousness, leading to treatment discontinuation, leading to dose interruption/adjustment, requiring additional therapy, requiring immunosuppressive medication and leading to fatal outcome. In

addition, a summary of serious adverse events with number of occurrences will be produced (an occurrence is defined as >1 day between start and prior end date of record of same preferred term).

For the legal requirements of ClinicalTrials.gov and EudraCT, two required tables on on-treatment adverse events which are not serious adverse events with an incidence greater than 5% and on on-treatment serious adverse events and SAE suspected to be related to study treatment will be provided by system organ class and preferred term on the safety set population.

If for a same patient, several consecutive AEs (irrespective of study treatment causality, seriousness and severity) occurred with the same SOC and PT:

- a single occurrence will be counted if there is ≤ 1 day gap between the end date of the preceding AE and the start date of the consecutive AE
- more than one occurrence will be counted if there is > 1 day gap between the end date of the preceding AE and the start date of the consecutive AE

For occurrence, the presence of at least one SAE / SAE suspected to be related to study treatment / non SAE has to be checked in a block e.g., among AE's in a ≤ 1 day gap block, if at least one SAE is occurring, then one occurrence is calculated for that SAE.

The number of deaths resulting from SAEs suspected to be related to study treatment and SAEs irrespective of study treatment relationship will be provided by SOC and PT.

2.8.1.1 Adverse events of special interest / grouping of AEs

Data analysis of AESIs

An adverse event of special interest (AESI) is a grouping of adverse events that are of scientific and medical concern specific to compound PDR001. These groupings are defined using MedDRA terms, SMQs (standardized MedDRA queries), HGLTs (high level group terms), HLT (high level terms) and PTs (preferred terms). Customized SMQs (Novartis MedDRA queries, NMQ) may also be used. A NMQ is a customized group of search terms which defines a medical concept for which there is no official SMQ available or the available SMQ does not completely fit the need. It may include a combination of single terms and/or an existing SMQ, narrow or broad.

For each specified AESI, number and percentage of patients with at least one event of the AESI occurring during on treatment period will be summarized.

Summaries of these AESIs will be provided (specifying grade, SAE, relationship, leading to treatment discontinuation, leading to dose adjustment/interruption, hospitalization, death, requiring immunosuppressive medication etc.). Additional summaries will be provided to report all AESIs, AESIs related to study treatment, all serious AESIs and serious AESIs related to study treatment collected during the on-treatment period and up to 150 days after last administration of PDR001.

A listing of all grouping levels down to the MedDRA preferred terms used to define each AESI will be generated.

2.8.2 Deaths

Separate summaries for on-treatment and all deaths will be produced by system organ class and preferred term. Additional summary will be displayed to report all deaths up to 150 days after last administration of PDR001.

All deaths will be listed, post treatment deaths will be flagged. A separate listing of deaths prior to starting treatment will be provided for all screened subjects.

2.8.3 Laboratory data

On analyzing laboratory, data from all sources (central and local laboratories) will be combined. The summaries will include all assessments available for the lab parameter collected no later than 150 days after the last study treatment administration date (see Section 2.1.1).

The following summaries will be produced for hematology and biochemistry laboratory data (by laboratory parameter and treatment):

- Worst post-baseline CTC grade (regardless of the baseline status). Each subject will be counted only for the worst grade observed post-baseline.
- Shift tables using CTC grades to compare baseline to the worst on-treatment value
- For laboratory tests where CTC grades are not defined, shift tables using the low/normal/high/(low and high) classification to compare baseline to the worst on-treatment value.
- Trends of lab parameter values over time (baseline and selected on-treatment timepoints) should be displayed via boxplots based on time windows and corresponding tables displaying the statistics used for the box plots by the selected time points.

The following listing will be produced for the laboratory data:

- Listing of all CTC grade 3 or 4 laboratory toxicities

Liver function parameters

Liver function parameters of interest are total bilirubin (TBL), ALT, AST and alkaline phosphatase (ALP). The number (%) of patients with worst post-baseline values as per Novartis Liver Toxicity guidelines will be summarized:

The following summaries will be produced:

- ALT or AST > 3xULN
- ALT or AST > 5xULN
- ALT or AST > 8xULN
- ALT or AST > 10xULN
- ALT or AST > 20xULN
- TBL > 2xULN
- TBL > 3xULN

- ALT or AST > 3xULN & TBL > 2xULN
- ALT or AST > 3xULN & TBL > 2xULN & ALP < 2xULN

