2.1 Data analysis general information

The interim and final analyses will be performed by Novartis. SAS version 9.4 or later software will be used to perform all data analyses and to generate tables, figures and listings.

There are 1 interim and a primary analysis planned for the primary efficacy endpoint.

The analysis cut-off date for the interim analysis will be established after 30 enrolled patients have completed 3 radiological assessments (approximately after 24 weeks of treatment) or have shown disease progression or have discontinued efficacy follow-up for any other reason. The analysis cut-off date for the primary analysis of study data will be 1 year after LPFT in the initially enrolled well-differentiated NET group. The primary analysis data will be summarized in the clinical study report (CSR).

For each of the analyses, all statistical analyses will be performed using all data collected in the database up to the data cutoff date. All data with an assessment date or event start date (e.g. vital sign assessment date or start date of an adverse event) prior to or on the cut-off date will be included in the analysis. Any data collected beyond the cut-off date will not be included in the analysis and will not be used for any derivations.

All events with start date before or on the cut-off date and end date after the cut-off date will be reported as ongoing. The same rule will be applied to events starting before or on the cut-off date and not having documented end date. This approach applies, in particular, to adverse event

and concomitant medication reports. For these events, the end date will not be imputed and therefore will not appear in the listings.

All analyses will be performed separately for the two groups of well-differentiated NET and poorly-differentiated GEP-NEC unless otherwise specified.

General analysis conventions

Pooling of centers: Unless specified otherwise, data from all study centers will be pooled for the analysis. Due to expected small number of patients enrolled at centers, no center effect will be assessed.

Qualitative data (e.g., gender, race, etc.) will be summarized by means of contingency tables; a missing category will be included as applicable. Percentages will be calculated using the number of patients in the relevant population or subgroup as the denominator.

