For safety and efficacy evaluations, the last available assessment on or before the date of start of study treatment is defined as “baseline” assessment.

If patients have no value as defined above, the baseline result will be missing.

On-treatment assessment/event and observation periods

For adverse event reporting the overall observation period will be divided into three mutually exclusive segments:

1. ***pre-treatment period***: from day of patient’s informed consent to the day before first administration of study treatment
2. ***on-treatment period***: from date of first administration of study treatment to 30 days after date of last actual administration of any study treatment (including start and stop date)
3. ***post-treatment period***: starting at day 31 after last administration of study treatment.

Safety summaries (tables, figures) include only data from the on-treatment period with the exception of baseline data which will also be summarized where appropriate (e.g. change from baseline summaries). In addition, a separate summary for death including on treatment and post treatment deaths will be provided. In particular, summary tables for adverse events (AEs) will summarize only on-treatment events, with a start date during the on-treatment period (***treatment-emergent*** AEs).

Additional summaries will be displayed to report deaths, all AEs, AEs related to study treatment, all SAEs and SAEs related to study treatment collected up to 150 days after last administration of PDR001.

However, all safety data (including those from the post-treatment period) will be listed and those collected during the pre-treatment and post-treatment period will be flagged.

Last contact date

The last contact date will be derived for patients not known to have died at the analysis cut-off using the last complete date among the following:

Table 2-1 Last contact date data sources

Source data	Conditions
Last contact date/last date patient was known to be alive from Survival Follow-up page	- Patient status is reported to be alive, lost to follow-up or unknown.
Start/End dates from further antineoplastic therapy	Non-missing medication/procedure term.
Start/End* dates from drug administration record	Non-missing dose. Doses of 0 are allowed.
End of treatment date from end of treatment page	No condition.
Tumor (RECIST/irRECIST) assessment date	Evaluation is marked as 'done'.

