5.1.2 AE, ConMeds and safety assessment date imputation

Table 5-1 Imputation of start dates (AE, CM) and assessments (LB, EG, VS)

Missing Element	Rule
day, month, and year	
 No imputation will be done for completely missing dates
day, month	
 If available year = year of study treatment start date then 
 If stop date contains a full date and stop date is earlier than study treatment start date then set start date = 01JanYYYY Else set start date = study treatment start date. If available year > year of study treatment start date then 01JanYYYY If available year < year of study treatment start date then 01JulYYYY
day	
 If available month and year = month and year of study treatment start date then 
 If stop date contains a full date and stop date is earlier than study treatment start date then set start date= 01MONYYYYY. Else set start date = study treatment start date. If available month and year > month and year of study treatment start date then 01MONYYYYY If available month and year < month year of study treatment start date then 15MONYYYYY

Table 5-2 Imputation of end dates (AE, CM)

Missing Element	Rule (* = last treatment date plus 150 days not > (death date, cut-off date, withdrawal of consent date))
day, month, and year	
 Completely missing end dates (incl. ongoing events) will be imputed by the end date of the on-treatment period*
day, month	
 If partial end date contains year only, set end date = earliest of 31DecYYYY or end date of the on-treatment period *
day	
 If partial end date contains month and year, set end date = earliest of last day of the month or end date of the on-treatment period*

Any AEs and ConMeds with partial/missing dates will be displayed as such in the data listings.

Any AEs and ConMeds which are continuing as per data cut-off will be shown as 'ongoing' rather than the end date provided.

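### SAP 2.8.3 gives the laboratory summaries a 150-day post-dose window that contradicts the 30-day on-treatment definition it cites, and Table 5-2 attaches 150 days to the same term

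*SAP*

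**What the plan says.** SAP 2.1.1 (General definitions) sets the on-treatment period as running "from date of first administration of study treatment to 30 days after date of last actual administration of any study treatment", with the post-treatment period "starting at day 31 after last administration of study treatment". It then gives a scope rule: "Safety summaries (tables, figures) include only data from the on-treatment period with the exception of baseline data". The 150-day exceptions named there are separate: "Additional summaries will be displayed to report deaths, all AEs, AEs related to study treatment, all SAEs and SAEs related to study treatment". Laboratory data are not among them. Protocol 10.5.3.1 has the same 30-day definition, and protocol 10.5.3.3 plans laboratory shift tables against the worst on-treatment value without any 150-day window.

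SAP 2.8.3 (Laboratory data) says its summaries use every available assessment "collected no later than 150 days after the last study treatment administration date" and refers the reader to 2.1.1. It then lists worst post-baseline CTC grade, shift tables to the worst on-treatment value, and liver-threshold counts based on worst post-baseline values.

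SAP 5.1.2, Table 5-2, imputes missing AE and medication end dates, including those of ongoing events, to the end of the on-treatment period. Its footnote gives that date as "last treatment date plus 150 days not > (death date, cut-off date, withdrawal of consent date". SAP 2.1 says of events ongoing at the cut-off that "the end date will not be imputed and therefore will not appear in the listings".

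SAP section 4 declares one change from the protocol, the dropped evaluation of heterogeneity between cohorts, and states that there are no others.

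**The concern.** One term carries two end points in the same SAP, and the laboratory section relies on a cross-reference that does not contain the rule it is cited for. Two programmers could follow the text faithfully and produce different shift tables.

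The extra window is also not neutral. Protocol 6.4.3 prohibits no therapy during post-treatment follow-up. For AEs, the protocol stops collecting unrelated events once a new antineoplastic drug starts between the 30-day and 150-day follow-ups (8.1.1). SAP 2.8.3 has no such stop for laboratory values, and grades are assigned from the observed value alone, without clinical assessment (SAP 5.3). A cytopenia or transaminase rise on the next line of chemotherapy could therefore appear in a PDR001 laboratory table, possibly under an on-treatment label.

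The Table 5-2 label creates a second problem. SAP 2.4.2 censors time to first immunosuppressive medication at the end of the on-treatment period, among other dates, and a reader who takes the definition from Table 5-2 would use the wrong day.

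**Working it through.** The plan states no figure to reproduce. The check sets the definitions side by side and does the window arithmetic.

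**Inputs**
- End of the on-treatment period: last dose + 30 days (SAP 2.1.1; protocol 10.5.3.1). Post-treatment starts on day 31.
- Laboratory summary limit: last dose + 150 days (SAP 2.8.3).
- Imputation bound for AE and medication end dates: last dose + 150 days, capped at death, cut-off or consent withdrawal (SAP Table 5-2).
- Last scheduled haematology and chemistry: the 30-day safety visit (protocol Table 7-1), window ±7 days (protocol 7.1). Later contacts are by telephone unless the patient happens to be on site; women of childbearing potential return at day 150 (protocol 7.1.7).
- Duration of immunosuppressive medication = last date − first date + 1 (SAP 2.4.2).

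**1. Size of the window conflict.** 150 − 30 = 120 days. Counted from the start of the post-treatment period, days 31 to 150 inclusive give 150 − 31 + 1 = 120.

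**2. How much of that holds scheduled data.** The latest permitted 30-day sample is at 30 + 7 = day 37, so scheduled values pass day 30 by at most 7 days. Haematology or chemistry from day 38 to day 150 would be unscheduled. One source is protocol 6.3.3, which follows patients whose treatment was interrupted or stopped for toxicity, after the first 30 days, at about 30-day intervals until resolution or stabilization.

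**3. Which tables are affected.**
- Worst post-baseline grade and liver thresholds: SAP 2.8.3 read directly gives 150 days; the scope rule in 2.1.1 gives 30.
- Shift tables: 2.8.3 gives 150 days for all laboratory summaries, but the word on-treatment points to 30. Either window can be defended from the text.

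**4. Effect of the Table 5-2 bound on a duration, before the caps.** Day 0 is the last dose and the end date is missing.
- Start on day 0: 30 − 0 + 1 = 31 days against 150 − 0 + 1 = 151.
- Start on day −28: 30 + 28 + 1 = 59 days against 150 + 28 + 1 = 179.
- Start on day 60: 30 − 60 + 1 = −29 days against 150 − 60 + 1 = 91.

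The last line matters for the repair. SAP 2.4.2 plans a summary of medications starting from 31 to 150 days after the last dose, and a 30-day imputation bound would end such a record before it began. The 150-day bound is workable; its name is what conflicts.

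**5. SAP 2.1 against Table 5-2.** SAP 2.1 says flatly that end dates of ongoing events are not imputed; Table 5-2 imputes them. SAP 5.1.2 adds that partial, missing and ongoing records are still shown as such in listings, so the two agree on listings and disagree on derivations.

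**The case against.** The best defence is that SAP 2.8.3 sets only an outer limit. On-treatment is already defined as 30 days, so the shift tables would use 30 days and the post-baseline tables 150. That reading is plausible, so it cannot be said that the shift tables will contain post-treatment values, only that they may. It does not rescue the worst-grade and liver tables, which the 2.1.1 scope rule also covers, and it leaves the cross-reference pointing at a rule that is not there.

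A second defence is that 2.1.1 introduces its three periods for adverse event reporting. True, but its scope rule then speaks of safety summaries in general. A third is that a long look-back suits a checkpoint inhibitor. That may be intended, but for AEs and deaths the SAP provides it through separate additional summaries, and the same route is open for laboratory data.

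Some stronger readings are tempting and not supported:
- *Imputed dates lengthen medication durations.* A drug truly continuing past day 30 would be truncated by a 30-day end date. The direction of any bias depends on why the date is missing, which the documents do not say. The summary is also produced only where relevant.
- *Late laboratory values come mainly from sick or re-treated patients.* This is an inference from the follow-up rules with no figure behind it. Some late values may track toxicity that began on treatment.
- *Combining local and central results is part of the fault.* Protocol 7.2.6.6 provides for recording local results in defined circumstances, and nothing contradicts the pooling.

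**Conclusion.** The inconsistency is real. SAP 2.8.3 departs from SAP 2.1.1 and from the protocol's on-treatment definition, cites 2.1.1 for a limit that section does not set for laboratory data, and is not declared as a change in section 4. Table 5-2 attaches a second meaning to the same term, and its imputation rule conflicts with SAP 2.1 outside the listings.

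The excess is at most 120 days after the on-treatment period ends. The documents do not show how many laboratory values or medication records fall there. The conclusion rests on reading the 2.1.1 scope rule as covering all safety tables, as its words do. Only descriptive safety outputs are touched. AE incidence on treatment is unaffected because it depends on start dates, and neither ORR nor duration of response is involved. The plan should be corrected, but the defect does not threaten the trial's main conclusions.

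**What to change.** - **SAP 2.8.3:** use the 30-day on-treatment window of 2.1.1 for the main laboratory tables (shift, worst grade, liver thresholds). If a 150-day laboratory view is wanted, present it as a separate, labelled additional summary and add laboratory data to the 150-day list in 2.1.1.
- **Table 5-2:** keep last dose plus 150 days with its caps, which matches how AEs and medications are collected, but rename it, for example end of 150-day safety follow-up.
- **SAP 2.4.2:** state that censoring of time to immunosuppressive medication uses the 30-day definition.
- **SAP 2.1:** say that end dates of ongoing events are imputed for derivations only and never shown in listings.

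The cost is SAP wording, plus one extra output if the 150-day view is kept. No new data are needed. Two limits remain. A 30-day visit sample taken on days 31 to 37 leaves the main tables and would appear only in listings or the additional display. The 30-day window also reduces, but does not remove, values drawn after a new therapy has started.

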8. Patient must have an Eastern Cooperative Oncology Group (ECOG) performance status 0-2.
9. Tumor biopsy material must be provided for all patients [REDACTED]:
- Well-differentiated (G1/2) NET: Biopsy material must be provided following the diagnosis of metastatic disease. The tumor sample must be collected from a metastatic site not previously irradiated and **should preferably be taken within 6 months but not more than 24 months prior to start of study treatment.**
- [REDACTED]

- Poorly-differentiated GEP-NEC: Biopsy material must be collected from the primary tumor or from a metastatic site not previously irradiated, **taken not more than 24 months prior to start of study treatment.**
10. Women of childbearing potential must have had a negative serum pregnancy test within 72 hours prior to the start of study treatment. Highly effective contraception must be used while on study.
 11. Patient is deemed by the investigator to have the ability and means to be compliant with the protocol (treatment and follow-up).
 12. Patient must meet the following laboratory values at the screening visit:
 - Absolute Neutrophil Count $\geq 1.5 \times 10^9/L$
 - Platelets $\geq 75 \times 10^9/L$
 - Hemoglobin (Hgb) ≥ 9 g/dL
 - Serum creatinine < 1.5 mg/dL
 - Total bilirubin ≤ 1.5 x ULN
 - Aspartate transaminase (AST) ≤ 3.0 x ULN, except for patients with liver metastasis, if AST ≤ 5.0 x ULN
 - Alanine transaminase (ALT) ≤ 3.0 x ULN, except for patients with liver metastasis, if ALT ≤ 5.0 x ULN

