6.3.3.1 Follow up on potential drug-induced liver injury (DILI) cases

Patients with transaminase increase combined with TBIL increase may be indicative of potential DILI, and should be considered as clinically important events.

The threshold for potential DILI may depend on the patient's baseline AST/ALT and TBIL value; patients meeting any of the following criteria will require further follow-up as outlined below:

- For patients with normal ALT and AST and TBIL value at baseline: AST or ALT > 3.0 x ULN combined with TBIL > 2.0 x ULN
- For patients with elevated AST or ALT or TBIL value at baseline: [AST or ALT > 2 x baseline AND > 3.0 x ULN] OR [AST or ALT > 8.0 x ULN], combined with [TBIL > 2 x baseline AND > 2.0 x ULN]

Medical review needs to ensure that liver test elevations are not caused by cholestasis, defined as ALP elevation > 2.0 x ULN with R value < 2 in patients without bone metastasis, or elevation of ALP liver fraction in patients with bone metastasis.

Note: (The R value is calculated by dividing the ALT by the ALP, using multiples of the ULN for both values. It denotes whether the relative pattern of ALT and/or ALP elevation is due to cholestatic ($R \leq 2$), hepatocellular ($R \geq 5$), or mixed ($R > 2$ and < 5) liver injury).

In the absence of cholestasis, these patients should be immediately discontinued from study drug treatment, and repeat LFT testing as soon as possible, preferably within 48 hours from the awareness of the abnormal results. The evaluation should include laboratory tests, detailed history, physical assessment and the possibility of liver metastasis or new liver lesions, obstructions/compressions, etc.

1. Laboratory tests should include ALT, AST, albumin, creatine kinase, total bilirubin, direct and indirect bilirubin, GGT, prothrombin time (PT)/INR and alkaline phosphatase.
2. A detailed history, including relevant information, such as review of ethanol, concomitant medications, herbal remedies, supplement consumption, history of any pre-existing liver conditions or risk factors, should be collected.
3. Further testing for acute hepatitis A, B, C or E infection and liver imaging (e.g. biliary tract) may be warranted.
4. Obtain PK sample, as close as possible to last dose of study drug, if PK analysis is performed in the study.

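### The combined ALT/AST-and-bilirubin rows in SAP 2.8.3 apply the protocol's normal-baseline limits to everyone, so they over-count against protocol 6.3.3.1 in patients who enter with raised liver tests, and their timing and ALP rules need stating

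*SAP*

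**What the plan says.** Under liver function parameters, SAP 2.8.3 states: "The number (%) of patients with worst post-baseline values as per Novartis Liver Toxicity guidelines will be summarized". The list that follows uses ULN multiples only. Its last two entries are combinations: "ALT or AST > 3xULN & TBL > 2xULN" and "ALT or AST > 3xULN & TBL > 2xULN & ALP < 2xULN". No baseline term or time window is given. The laboratory summaries reach well past treatment: "The summaries will include all assessments available for the lab parameter collected no later than 150 days after the last study treatment administration date".

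Protocol 6.3.3.1 says: "The threshold for potential DILI may depend on the patient's baseline AST/ALT and TBIL value". With ALT, AST and bilirubin all normal at baseline, its rule is "AST or ALT > 3.0 x ULN combined with TBIL > 2.0 x ULN", the same limits as the SAP row. Otherwise it changes: "For patients with elevated AST or ALT or TBIL value at baseline: [AST or ALT > 2 x baseline AND > 3.0 x ULN", or above 8×ULN, together with bilirubin above twice baseline and above 2×ULN. Cholestasis has to be excluded. It is defined by ALP above 2×ULN with R (ALT over ALP, each in ULN multiples) below 2 in patients without bone metastasis, and by the liver fraction of ALP in patients with bone metastasis.

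Inclusion criterion 12 (protocol 5.2) admits ALT and AST up to 3×ULN, "except for patients with liver metastasis, if ALT ≤ 5.0 x ULN" (likewise for AST), and bilirubin up to 1.5×ULN. It sets no ALP limit.

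**The concern.** The SAP takes the protocol's normal-baseline limits and applies them to all patients, in a population where raised entry values are allowed and liver metastases are expected. A patient who enters with ALT above 3×ULN meets the transaminase half of the row with no change on treatment. Only a bilirubin rise, which tumour progression in the liver could produce, is then needed to be counted.

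The study has no control arm against which such counts could be offset, and the groups are small. The clinical study report could show a combined-row count that differs from the protocol's potential-DILI rule with nothing to explain the difference.

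**Working it through.** The documents give no count or rate for these rows, so there is no planned figure to reproduce. The check compares the two rules. All values are multiples of ULN.

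**Limits by baseline.** For baseline ALT or AST *b*, the protocol limit is 3 if all three tests are normal at baseline, otherwise min(max(2*b*, 3), 8). For baseline bilirubin *t*, it is max(2*t*, 2). The SAP limits are always 3 and 2.

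| Baseline ALT/AST | Protocol limit | SAP limit |
|---|---|---|
| 1.0 | 3 | 3 |
| 1.5 | max(3, 3) = 3 | 3 |
| 2 | 4 | 3 |
| 3 | 6 | 3 |
| 4 | 8 | 3 |
| 5 | min(10, 8) = 8 | 3 |

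| Baseline bilirubin | Protocol limit | SAP limit |
|---|---|---|
| 1.0 | 2 | 2 |
| 1.2 | 2.4 | 2 |
| 1.5 | 3.0 | 2 |

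The rules part company once baseline ALT/AST exceeds 1.5 or baseline bilirubin exceeds 1.0. The first of these does not require liver metastases, since other patients may enter with ALT or AST up to 3.

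**Direction, first combined row.** Every route to a protocol-positive result requires ALT/AST above 3 and bilirubin above 2. A protocol-positive patient is therefore always in this row, and the row can only over-count. A same-day grid of eligible baselines (ALT 0.2 to 5.0, bilirubin 0.1 to 1.5) and later values (ALT up to 20, bilirubin up to 8) agrees: no discordant point at normal baseline, no protocol-positive point missed, and every discordant point an over-count at a raised baseline.

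**Example A, baseline.** Entry ALT 4 and bilirubin 1.2; later ALT 4.2, bilirubin 2.1, ALP 1.0 on one day. SAP: 4.2 > 3, 2.1 > 2 and 1.0 < 2, so both rows count the patient. Protocol: 4.2 is below 8 and 2.1 is below 2.4, so the rule is not met.

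**Example B, timing.** ALT 3.5 at week 8 and bilirubin 2.5 at week 40, each normal at the other visit. Worst values paired: positive. Same-day values: negative.

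**Example C, ALP row.** Normal baseline; ALT 12, bilirubin 3, ALP 2.5. R = 12/2.5 = 4.8, so without bone metastasis this is not cholestasis under the protocol, and the protocol rule is met. The first SAP row counts the patient; the ALP row drops the patient because 2.5 is not below 2. If worst ALP means the highest value at any time, a later ALP rise would also remove a patient whose ALP was below 2 at the event.

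**Scale of one patient.** With the group sizes in protocol 1.2.1.2, one misclassified patient is 1/21 = 4.8% in GEP-NEC, 1/95 = 1.1% in well-differentiated NET and 1/116 = 0.9% overall. This is a unit of measure, not an estimate of how many there would be.

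**The case against.** The SAP calls these rows neither Hy's law nor DILI. They close a descriptive laboratory list. Potential DILI under the protocol needs repeat confirmation and no alternative cause, and is then reported as an SAE; SAP 2.8.1 tabulates SAEs up to 150 days, and hepatitis is an event of special interest. Over-inclusion is the cautious direction for a screen. Shift tables show each test against baseline, and protocol 10.5.3.3 plans a listing of all laboratory data. The SAP also refers to a sponsor guideline that may fix the timing.

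Much of this stands, and it rules out some stronger readings:

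- A reader might infer that the trial will miscount drug-induced liver injury itself. The documents do not support that, because confirmed cases reach the report by the SAE route.
- A reader might infer that pairing values from different dates contradicts the protocol. Protocol 6.3.3.1 joins the two elevations without a time window, so this is a weakness of the SAP's literal rule and not a proven conflict. The sponsor guideline is not in the documents, so it cannot settle the matter either way.
- A reader might infer that one or two false positives would make up the whole liver signal. That holds only if there are no true cases, and the documents give no liver data.

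What the objection does not answer is the combined count. Shift tables take one test at a time. The only listing named in SAP 2.8.3 covers grades 3 and 4, whereas ALT 4.2×ULN and bilirubin 2.1×ULN are both grade 2 in SAP Table 5-3. The SAE tables do not correct the laboratory rows, and a full data listing leaves the reader to apply the protocol rule by hand. The limits match the protocol's normal-baseline DILI rule, and protocol Table 6-3 sends patients meeting Hy's law to that same section, so readers will probably take the rows in that sense.

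**Conclusion.** The point holds in limited form. The first combined row applies limits that are too low, by the protocol's own rule, for patients entering with ALT/AST above 1.5×ULN or bilirubin above 1.0×ULN. There it can only over-count. It matches the protocol at normal baselines on same-day values. The ALP row departs from the protocol's cholestasis rule and can drop protocol-positive patients. The timing rule is unspecified in both documents.

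For entry ALT of 3 to 5×ULN, the gap is 3×ULN in the SAP against 6 to 8×ULN in the protocol. How many patients this affects is unknown, because the documents do not report baseline liver tests or liver metastases. The conclusion assumes that the rows are programmed as listed in SAP 2.8.3 and that the unseen guideline adds no baseline term. No efficacy endpoint or success criterion is affected. This is an inexpensive improvement to a descriptive safety table.

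**What to change.** In SAP 2.8.3:

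1. Keep the ULN-only rows as a display.
2. Add a combined row using the baseline-dependent limits of protocol 6.3.3.1, with a patient listing that shows baseline and event values and dates.
3. Require the ALT/AST, bilirubin and ALP criteria to be met at the same assessment or within a stated short window. Because the protocol has no window, say that this is an analysis convention.
4. Reconcile the ALP criterion with the protocol's R-value and liver-fraction rule. If the liver fraction is not in the database, say how patients with bone metastasis are handled.

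The cost is a few lines of SAP text, minor programming and one or two more table rows. The ALT, AST, bilirubin and ALP values are already collected.
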